6.2.3 Visit 3/Day 8/Week 1: 7(± 4 days) after Visit 2 (QD treatment)

Subjects should not apply the study medication within 6 hours prior to these visits.

At Visit 3, the investigator or designee will perform the following procedures:

1. Query the subject in a non-directive manner about any changes in her/his health since the previous visit and report all AEs as appropriate
2. Query the subject about any changes in her/his concomitant therapies since the previous visit and report changes as appropriate
3. Confirm the subject has followed all study instructions
4. Confirm the location of each Target cNF
5. Have the subject perform an LTA of the symptoms for each Target cNF
6. The investigator will perform an LTA of the signs for each Target cNF
7. Weigh study medication
8. Collect and dispense study medication as appropriate
9. Review the study instructions, including application technique and Target cNF locations, with the subject
10. Schedule the next study visit.
11. Remind subject to apply study medication 4 (\pm 2) hours prior to Visit 4

6.2.4 Visit 4/Day 29/Week 4: 28 (\pm 4 days) after Visit 2 (QD treatment)

Only at select sites participating in Pharmacokinetic sampling: At Visit 4, subjects must apply the study medication 4 (\pm 2) hours prior to this visit.

At sites NOT participating in Pharmacokinetic sampling: At Visit 4, subjects should not apply the study medication within 6 hours prior to this visit.

At Visit 4, the investigator or designee will perform the following procedures:

1. Query the subject in a non-directive manner about any changes in her/his health since the previous visit and report all AEs as appropriate
2. Query the subject about any changes in her/his concomitant therapies since the previous visit and report changes as appropriate
3. Confirm the subject has followed all study instructions
4. Collect samples for clinical laboratory tests and pharmacokinetics
5. Record date and time of last study medication application
6. Record 24-hour time of pharmacokinetic sample collection
7. Perform a urine pregnancy test for WOCBP
8. Confirm the location of each Target cNF
9. **FOR EACH TARGET cNF:**
 - Perform a PTA
 - Have the subject perform an SSA
 - Measure the dimensions
10. Have the subject perform an LTA of the symptoms for each Target cNF
11. The investigator will perform an LTA of the signs for each Target cNF
12. Weigh study medication
13. Collect and dispense study medication as appropriate
14. Review the study instructions, including application technique and Target cNF locations, with the subject
15. Schedule the next study visit.

6.2.5 Visit 5/Day 57/Week 8: 56 (± 4 days) after Visit 2 (QD treatment)

Subjects should not apply the study medication within 6 hours prior to this visit.

At Visit 5, the investigator or designee will perform the following procedures:

1. Query the subject in a non-directive manner about any changes in her/his health since the previous visit and report all AEs as appropriate
2. Query the subject about any changes in her/his concomitant therapies since the previous visit and report changes as appropriate
3. Confirm the subject has followed all study instructions
4. Perform a urine pregnancy test for WOCBP
5. Confirm the location of each Target cNF
6. **FOR EACH TARGET cNF:**
 - Perform a PTA
 - Have the subject perform an SSA
 - Measure the dimensions
7. Have the subject perform an LTA of the symptoms for each Target cNF
8. The investigator will perform an LTA of the signs for each Target cNF
9. Weigh study medication
10. Collect and dispense study medication as appropriate
11. Review the study instructions, including application technique and Target cNF locations, with the subject
12. Schedule the next study visit.

6.2.6 Visit 6/Day 85/Week 12: 84 (± 4 days) after Visit 2 (QD treatment)

Subjects should not apply the study medication within 6 hours prior to this study visit.

At Visit 6, the investigator or designee will perform the following procedures:

1. Query the subject in a non-directive manner about any changes in her/his health since the previous visit and report all AEs as appropriate
2. Query the subject about any changes in her/his concomitant therapies since the previous visit and report changes as appropriate
3. Confirm the subject has followed all study instructions
4. Perform a urine pregnancy test for WOCBP
5. Confirm the location of each Target cNF
6. Perform a PTA for each Target cNF
7. Have the subject perform a SSA for each Target cNF
8. Have the subject perform a PROM for each Target cNF
9. Have the subject perform an LTA of the symptoms for each Target cNF
10. The investigator will perform an LTA of the signs for each Target cNF
11. Measure the dimensions of each Target cNF
12. Take standardized photographs of each Target cNF
13. Weigh study medication
14. Collect and dispense study medication as appropriate
15. Review the study instructions, including application technique and Target cNF locations, with the subject

16. Schedule the next study visit.

6.2.7 Visit 7/Day 141/Week 20: 140 (± 4 days) after Visit 2 (QD treatment)

Subjects should not apply the study medication within 6 hours prior to this visit.

At Visit 7, the investigator or designee will perform the following procedures:

1. Query the subject in a non-directive manner about any changes in her/his health since the previous visit and report all AEs as appropriate
2. Query the subject about any changes in her/his concomitant therapies since the previous visit and report changes as appropriate
3. Confirm the subject has followed all study instructions
4. Perform a urine pregnancy test for WOCBP
5. Confirm the location of each Target cNF
6. **FOR EACH TARGET cNF:**
 - Perform a PTA
 - Have the subject perform an SSA
 - Measure the dimensions
7. Have the subject perform an LTA of the symptoms for each Target cNF
8. The investigator will perform an LTA of the signs for each Target cNF
9. Weigh study medication
10. Collect and dispense study medication as appropriate
11. Review the study instructions, including application technique and Target cNF locations, with the subject
12. Schedule the next study visit.

6.2.8 Visit 8/Day 183/Week 26 (End of QD treatment; start of no treatment follow-up; early termination if subject discontinues from the study prior to Visit 8)

This visit must occur 182 days (± 4 days) after Visit 2.

Subjects should not apply the study medication within 6 hours prior to this study visit.

At this visit, the investigator or designee will perform the following procedures:

1. Query the subject in a non-directive manner about any changes in her/his health since the previous visit and report all AEs as appropriate
2. Query the subject about any changes in her/his concomitant therapies since the previous visit and report changes as appropriate
3. Confirm the subject has followed all study instructions
4. Measure vital signs
5. Collect samples for clinical laboratory tests
6. Perform a urine pregnancy test for WOCBP
7. Confirm the location of each Target cNF
8. Perform a PTA for each Target cNF
9. Have the subject perform a SSA for each Target cNF
10. Have the subject perform a PROM for each Target cNF
11. Have the subject perform an LTA of the symptoms for each Target cNF
12. The investigator will perform an LTA of the signs for each Target cNF

13. Measure the dimensions of each Target cNF
14. Take standardized photographs of each Target cNF
15. Weigh study medication
16. Collect all study medication
17. Review the study instructions with the subject. If the subject wishes to be contacted about participation in the exit interview study inform the identified individual at the exit interview vendor that the subject has completed study participation and provide them with the subject's contact information
18. Schedule the next study visit.

6.2.9 Visit 9/Day 211/Week 30 (End of study, early termination if subject completes Visit 8 and discontinues from the study prior to Visit 9)

This visit must occur 210 days (± 4 days) after Visit 2.

At this visit, the investigator or designee will perform the following procedures:

1. Query the subject in a non-directive manner about any changes in her/his health since the previous visit and report all AEs as appropriate
2. Query the subject about any changes in her/his concomitant therapies since the previous visit and report changes as appropriate
3. Confirm the subject has followed all study instructions
4. Measure vital signs
5. Perform a urine pregnancy test for WOCBP
6. Confirm the location of each Target cNF
7. Have the subject perform an LTA of the symptoms for each Target cNF
8. The investigator will perform an LTA of the signs for each Target cNF
9. Measure the dimensions of each Target cNF
10. Take standardized photographs of each Target cNF
11. Perform a PTA for each Target cNF
12. Have the subject perform a SSA for each Target cNF
13. Discharge the subject from the study.

6.2.10 *Unscheduled Visit*

The investigator may see a subject for an unscheduled study visit at any time it is necessary, in the investigator's opinion.

At unscheduled visits, the investigator or designee will perform the following procedures, at a minimum:

1. Query the subject in a non-directive manner about any changes in her/his health since the previous visit and report all AEs as appropriate
2. Query the subject about any changes in her/his concomitant therapies since the previous visit and report changes as appropriate
3. Review the study instructions with the subject
4. Schedule the next study visit.

Complete other study procedures that are, in the investigator's opinion, appropriate for the visit. Detailed instructions for documenting unscheduled visits will be included in the CRF completion guidelines.

6.3 **Target cNF identification**

At Visit 1 the investigator will identify 10 clinically diagnosed Target cNFs. Preferably 2 Target cNFs are located on the face and 8 Target cNFs are located on the anterior trunk or upper extremities. Alternatively, at least 1 Target cNF is located on the face, in which case 9 Target cNFs must be located on the anterior trunk or upper extremities.

For this study, the face, anterior trunk, and upper extremities are defined as follows:

- Face:
 - Vertically from the mandibular ridge to the hairline (for subjects with a receding hair the hairline is defined by a vertical line drawn coronally from tragus to tragus)
 - Horizontally from tragus to tragus, excluding the eyelids, eyebrows, and areas within 1 cm of the orbital rim.
- Anterior trunk:
 - The front of the torso down to the beltline, excluding the neck
- Upper extremities:
 - Arms from the shoulders to the wrist, (excluding the hands).

[figure not shown]
At Visit 1 each of the 10 clinically diagnosed Target cNFs must meet the following criteria for the subject to be enrolled:

- Has, in the investigator's opinion, a clinically typical appearance
- Is not within 1 cm of the orbital rim

- Is not covered with hair that might, in the investigator's opinion, interfere with obtaining photographs or impair evaluation of the cNF
- Has a PTA grade ≥ 2
- Is dome shaped
- Is not pedunculated
- Is a discrete cNF surrounded by sufficient non-affected skin that, in the investigator's opinion:
 - i. The dimensions can be measured
 - ii. The perimeter can be outlined in the study photographs
- Is not irritated (*e.g.*, bleeding, inflamed)
- Is not in an area subject to repeated trauma (*e.g.*, on the beltline, under a bra strap, etc.)
- Does not have an active cutaneous infection
- Target cNFs on the anterior trunk or upper extremities must have the following tumor dimensions:
 - i. Has a length that is $\geq 7\text{mm}$ and $\leq 14\text{mm}$
 - ii. Has a width that is $\geq 5\text{mm}$ and $\leq 14\text{mm}$
 - iii. Has a height that is $\geq 2\text{mm}$.
- Target cNFs on the face must have the following tumor dimensions:
 - i. Has a length that is $\geq 5\text{mm}$ and $\leq 14\text{mm}$
 - ii. Has a width that is $\geq 5\text{mm}$ and $\leq 14\text{mm}$
 - iii. Has a height that is $\geq 2\text{mm}$

Number the Target cNFs at Visit 1 starting with 1 and proceeding up to 10 with no number omitted or reused. Target cNFs 1 and 2 must be on the face and Target cNFs 3-10 must be on the anterior trunk or upper extremities. If only 1 Target cNF is identified on the face, Target cNF 1 must be on the face and Target cNFs 2-10 must be on the anterior trunk or upper extremities.

For identification in the study photographs with the Target cNF centered in the large template cutout place 2 appropriately numbered Identification (ID) stickers in the small template cutouts (diagram not to scale):

Write the Target cNF Number on at least one ID sticker. Both ID stickers must be visible in the photographs.

The investigator will document the location of each Target cNF on the Visit 1 body charts using the following process:

- Make a circle or similar mark identifying the location of each Target cNF
- Write the Target cNF Number adjacent to the mark
- Also report at least the following additional information on the body charts:
 - Protocol number
 - Subject Identifier.

At Visit 1 and Visit 2, the investigator or designee will dispense a photocopy of the body charts to the subject. New, eligible Target cNF(s) may be selected at Visit 2 if necessary. The investigator or designee will place the original Visit 1 and Visit 2 body charts in the subject's study file.

The investigator or designee must report the approximate location of each Target cNF identified at Visit 1 in the CRFs and include the Target cNF Number.

At Visit 2, the investigator will use the Visit 1 body charts and photographs to identify the location of the 10 Target cNFs identified at Visit 1. If the 10 Target cNFs identified at Visit 1 don't meet eligibility criteria, new eligible Target cNF(s) may be selected at Visit 2.

At Visits 3-9, prior to any Target cNF assessments, an investigational center staff member other than the evaluating investigator will use the Visit 2 body charts and study photographs to identify the location each Target cNF for the study evaluations. A staff member will use the cNF template, center each Target cNF in the large circular cutout and place the 2 ID stickers, numbered as appropriate on the subject's skin.

The investigator is not allowed to participate in the photography process or to use the study photographs to assist with any Target cNF evaluations EXCEPT as noted below:

The investigator may view the Visit 2 photographs, and only the Visit 2 photographs, to assist with determining the location of the Target cNFs at Visits 3-9 only if there is no other option to locate the cNFs. If the investigator views the Visit 2 photographs the details of the situation must be reported in the subject's study file and on the CRFs.

7 STUDY ASSESSMENTS

The study assessments will be performed according to the schedules noted below by the investigator, an appropriately trained investigational center staff member or the subject as noted for each assessment. **The same staff member should perform the assessments for a given subject throughout the study.** If this becomes impossible, appropriate designee with overlapping experience with the study and the subject should perform the assessments.

7.1 Safety assessments

7.1.1 Adverse Event Assessments

Information regarding occurrence of AEs will be captured throughout the study. The study site visits are designed to ensure any untoward events in subjects are quickly identified by the investigator and can be treated promptly. Duration, severity/grade, outcome, treatment, and relationship to study medication will be recorded.

7.1.2 Clinical Laboratory Evaluations

At Visits 1, 2 (prior to the randomization), 4 and 8, a qualified investigational center staff member will collect non-fasting blood and urine samples for clinical laboratory analysis. The following tests, at a minimum, will be conducted:

Chemistry Panel

Albumin
Alkaline phosphatase
Alanine aminotransferase (ALT)
Aspartate aminotransferase (AST)
Blood urea nitrogen (BUN)
Bicarbonate
Calcium
Chloride
Creatinine
Glucose
Lactate dehydrogenase (LDH)
Phosphorus
Potassium
Sodium
Total bilirubin
Total protein
Uric acid

Complete Blood Count

Hematocrit
Hemoglobin
Platelet count
Red blood cell morphology
Red blood cell count
White blood cell count
White blood cell differential
% & absolute
Basophils
Eosinophils
Lymphocytes
Monocytes
Neutrophils

Urinalysis with Microscopic

The results of the clinical laboratory analysis will be reported on the laboratory's standard reports. The investigator must note NCR or clinically relevant (CR) to define the clinical relevance of any result that is outside the normal range for the laboratory. The investigator must date and sign/initial every laboratory report.

The investigator must review each subject's Visit 1 laboratory reports prior to Visit 2. The subject must not be randomized if any of the Visit 1 results are outside normal range for the laboratory AND, in the opinion of the investigator, CR. The investigator must review all laboratory reports in a timely manner.

The investigator must report all laboratory results that are BOTH outside the normal range for the laboratory AND, in the opinion of the investigator, CR as medical history if found prior to the first study medication application or as an AE if found after the first study medication application begins.

The total number of venipunctures and the total volume of blood collected during the study will be limited to that need for the safety monitoring. Refer to the laboratory manual(s) for the collection procedures and the total volume of blood collected.

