5.6.4 Subject randomization

At Visit 2, the investigator will determine the subject's eligibility for randomization to study medication. To be eligible for randomization the subject must:

- Have a PTA ≥ 2 for all Target cNFs
- Have clinical laboratory test results for all measured analytes at Visit 1 and all results are either within the range of normal for the laboratory or, any abnormal results, are defined as Not Clinically Relevant (NCR) by the investigator.
- Have, if a Woman of Childbearing Potential (WOCBP), a negative urine pregnancy test result at Visit 2.
- Have NOT used any topical or system therapies within the specified period prior to Visit 2 per the exclusion criteria

The investigator or designee will assign study medication to eligible subjects by selecting the

Subject Kits in chronological sequence in ascending numerical order starting with the lowest available Subject Kit number. The investigator will not omit or reuse any Subject Kit number.

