6.2.2 Visit 2/Day 1/Week 0 (Randomization; start of QD treatment)

Visit 2 must occur within 28 days (4 weeks) after Visit 1.

Subsequent study visit dates must be scheduled based on the date of this visit.

This visit may be combined with Visit 1 and only with advance Sponsor approval. If combined with Visit 1, central laboratory samples must be collected along with local laboratory samples.

Randomization must not occur until the investigator reviews the subject's Visit 1 clinical laboratory test results or local laboratory test results, if applicable.

At this visit, the investigator or designee will perform the following procedures PRIOR TO RANDOMIZATION:

1. Query the subject in a non-directive manner about any changes in her/his health since the previous visit and report any changes as medical history

2. Query the subject about any changes in her/his concomitant therapies since the previous visit and report changes as appropriate
3. Confirm the subject meets all inclusion criteria and no exclusion criteria
4. Confirm the subject has followed all study instructions
5. Perform a urine pregnancy test for WOCBP
6. Collect Visit 1 body charts
7. Create Visit 2 body charts and dispense a photocopy to the subject
8. Confirm the location of each Target cNF identified
9. Measure the dimensions of each Target cNF
10. Have the subject perform a Subject's Self-Assessment (SSA) for each Target cNF
11. Perform a PTA for each Target cNF
12. Confirm subject is eligible for randomization, discharge subjects who are not eligible from the study.

Determine the subject's eligibility for randomization. Ineligible subjects must be discontinued from the study. For eligible subjects the investigator or designee will perform the following procedures:

1. Have the subject perform a pre-application Local Tolerability Assessment (LTA) of the symptoms for each Target cNF
2. Have the subject perform a Patient Reported Outcome Measure (PROM) for each Target cNF
3. The investigator will perform a pre-application LTA of the signs for each Target cNF
4. Take standardized photographs of each Target cNF
5. Measure vital signs
6. Collect samples for clinical laboratory tests
7. Randomize eligible subjects
8. Weigh study medication tube pre first study medication application and record weight
9. An investigational center staff member must:
 - Instruct the subject on the proper study medication application technique

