8.1 Definitions

8.1.1 Adverse Event (AE)

An AE is any untoward medical occurrence in a patient or clinical investigation subject administered a pharmaceutical product and which does not necessarily have a causal relationship with this treatment. An AE can therefore be any unfavorable and unintended sign or symptom associated with the use of an investigational product (including an abnormal laboratory finding), whether or not related to the investigational product.

Thus, any new, CR worsening of an existing sign, symptom, or disease, should be considered an AE.

Worsening of any Target cNF study assessment (e.g., LTA signs and symptoms) should be reported as an AE only if the use of the study medication is interrupted or discontinued or other therapy is required to manage the event.

Every new episode or clinically relevant worsening of a chronic condition (e.g., headaches, allergies, depression, and hypertension) should be reported as a separate AE, even if the condition is reported in the subject's medical history.

The investigator should, when certain, report a diagnosis rather than the signs, symptoms or clinically relevant abnormal laboratory values associated with the AE. Otherwise, signs, symptoms or abnormal laboratory values may be used to describe the AE.

An abnormality (*e.g.*, clinically relevant laboratory abnormalities) discovered prior to the first study medication application, should be reported as medical history, not as an AE.

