9.3.6 Safety Analyses

Subjects will be assessed for the occurrence of new and ongoing AEs. Descriptions of AEs will include the dates of onset and resolution (if resolved), maximum severity, seriousness, and action taken regarding the study drug, corrective treatment, outcome, and investigator's assessment of causality. All AEs will be recorded and classified using terminology from the Medical Dictionary for Regulatory Activities (MedDRA). All reported treatment-emergent AEs (TEAEs), defined as any AE with an onset on or after the date of first study drug application, will be summarized by treatment group, the number of subjects reporting TEAEs, system organ class, preferred term, severity, and relationship to study drug. When summarizing TEAEs by severity or relationship to study drug, each subject will be counted only once within a system organ class or a preferred term using the event with the greatest severity or causality, respectively, within each category. All reported SAEs will be summarized by treatment group, the number of subjects reporting SAEs, system organ class, preferred term, severity, and relationship to study drug.

All information pertaining to AEs noted during the study will be listed by subject and will include a verbatim description of the event as reported by the investigator, as well as the preferred term, system organ class, start date, stop date (if stopped), seriousness, severity, action taken regarding the study drug, corrective treatment, outcome, and relationship to the study drug. In addition, a listing of subjects who prematurely discontinued from the study due to AEs will be provided as well as a listing of subjects who reported an SAE.

Changes from baseline in safety laboratory values, local tolerability assessments, and vital sign measurements will be summarized with descriptive statistics for each treatment group at

all applicable study visits.

Shift tables will be presented for changes in safety laboratory values to summarize laboratory test results collected at all visits. Normal ranges established by the central laboratory will be used to determine the shifts. A listing of all out-of-range laboratory test results at any assessment time point will also be provided. Determination of clinical significance for all out-of-range laboratory values will be made by each investigator and included in the listing. In addition, a listing of all clinically significant laboratory test results will be provided.

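### Laboratory findings are sorted into medical history or AE by when they are found, so an abnormality in the pre-dose Visit 2 sample can be counted as treatment-emergent

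*Combined protocol and SAP*

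**What the plan says.** **Sampling.** Section 7.1.2: "At Visits 1, 2 (prior to the randomization), 4 and 8, a qualified investigational center staff member will collect non-fasting blood and urine samples". The Visit 2 sample is therefore a pre-dose sample.

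**Eligibility.** Section 5.6.4 requires the subject to "Have clinical laboratory test results for all measured analytes at Visit 1", each either normal or judged not clinically relevant. Section 6.2.2 adds: "Randomization must not occur until the investigator reviews the subject's Visit 1 clinical laboratory test results or local laboratory test results, if applicable". Neither section names the Visit 2 central result.

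**Combined visits.** With advance sponsor approval, Visits 1 and 2 may be one visit. Section 6.2.2: "If combined with Visit 1, central laboratory samples must be collected along with local laboratory samples".

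**Classification.** Under section 7.1.2, a result that is out of range and clinically relevant is medical history if found before the first application, and is reported "as an AE if found after the first study medication application begins". Section 8.1.1 says that an abnormality "discovered prior to the first study medication application, should be reported as medical history, not as an AE".

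**Treatment-emergent AEs.** Section 9.3.6, and the synopsis in the same terms, use "defined as any AE with an onset on or after the date of first study drug application".

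**Baseline and reporting period.** Section 9.3.4 describes Visit 1 and Visit 2 data as collected before treatment. Section 8.2.1 opens AE reporting at the start of the first application.

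**The concern.** The rule in 7.1.2 turns on when the investigator learns of a result. What matters for attribution is whether the sample was taken before or after exposure. For Visit 1, and for Visits 4 and 8, the two criteria normally agree. For the Visit 2 sample they can part: it is taken before any exposure but may well be read after it.

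Safety against vehicle is one of the two primary objectives. Section 8.1.4 lists kidney, liver, coagulation and immune events as being of special interest, and the panel in 7.1.2 includes creatinine, BUN, ALT, AST, bilirubin and the white cell count. An abnormality that preceded exposure could thus enter the AE tables, receive severity and causality ratings, and fall in an organ class of special interest. The same value seen at Visit 1 would have been medical history or would have kept the subject out.

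**Working it through.** The plan states no figure on this point, so the check is mainly a reading of the rules in the order in which they apply.

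1. **Order of events at Visit 2 (section 6.2.2).** Eligibility is settled first. In the list that follows for eligible subjects, laboratory sampling is step 6, randomization is step 7, and the supervised first application falls under step 9. No step waits for, or reviews, the step 6 result.
2. **When the result is read.** Turnaround is not given. With sampling and dosing in one visit and no review step, the central result will presumably often be read after dosing. A result that did come back before the first application would be medical history, and the problem would not arise.
3. **Classification (section 7.1.2).** A clinically relevant result found after the first application begins is an AE. There is no exception for a sample collected earlier.
4. **Treatment-emergent status (section 9.3.6 and synopsis).** The test is on the date, and it includes the day of first application. Draw and first application share Visit 2, Day 1. Dating onset to the draw gives Day 1, and dating it to the laboratory report gives Day 1 or later. Both qualify.
5. **Against the rest of the plan.** Section 9.3.4 calls the same data pre-treatment, and 8.2.1 starts AE reporting after the sample was taken. One Visit 2 value can thus be summarised as baseline and counted as a treatment-emergent AE.
6. **Who can be affected.** A clinically relevant abnormality at Visit 1 bars randomization (5.6.4, 7.1.2), and Visit 2 follows within 28 days. The affected subjects are those whose abnormality arises, or is first judged relevant, in that gap.
7. **Combined visits.** Local results are reviewed before randomization. An abnormality in the paired samples would normally show locally first and be handled before dosing. What remains is a central result that is abnormal where the local one was not.

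**Scale.** Inputs: about 168 randomized (section 9.1), allocation 1:1:1 (section 9.2), so 168 / 3 = 56 per arm. The rate p of a new clinically relevant Visit 2 result read after dosing is not in the documents and is assumed. Expected number = n × p; chance of at least one in an arm = 1 − (1 − p)^56.

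| Assumed p | Expected in 168 | Expected per arm of 56 | Chance of at least one in an arm |
|---|---|---|---|
| 1% | 1.68 | 0.56 | 0.43 |
| 2% | 3.36 | 1.12 | 0.68 |
| 3% | 5.04 | 1.68 | 0.82 |
| 5% | 8.40 | 2.80 | 0.94 |

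At 1% to 3% this is about 2 to 5 subjects in the trial. The 5% row only shows how the count scales.

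**The case against.** The strongest reply is that the plan does not compel misfiling. Section 8.1.1 defines an AE as an occurrence in someone who has been given the product and speaks of new, clinically relevant worsening; 8.2.1 begins reporting at first application; 9.3.4 treats Visit 2 data as baseline. A careful site could rely on these and file a pre-dose value as medical history. This stands in part: the sections pull in different directions. But 7.1.2 is the specific instruction for laboratory results and it is mandatory, so the site would have to override it. With about 27 centers, the same result could be filed both ways.

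A second reply is that the consequences are small. The sample precedes randomization, so misfiling does not depend on arm. AEs are reported in summaries and listings with no specified hypothesis test, and 9.3.6 sets out no separate analysis of special-interest events. Laboratory change and shift tables do not depend on how an AE is filed. All of this stands. A laboratory AE dated Day 1 can also be recognised in the listings, since the next scheduled sample is at Visit 4, but the summary tables would still count it.

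Four stronger readings are tempting, and the documents do not support them:

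- *That 8.1.1 also orders the AE classification.* It states only the medical-history half, for abnormalities discovered before dosing. Only 7.1.2 makes a later finding an AE.
- *That in combined visits every central baseline abnormality is misfiled.* The local results reviewed before randomization would usually reveal it first.
- *That the comparison with vehicle is biased or could be reversed.* Misfiling is balanced across arms in expectation, and no AE test is specified that it could reverse.
- *That leaving the Visit 2 sample out of eligibility is itself an error.* Screening on Visit 1 and drawing a baseline sample at Visit 2 is a coherent design.

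**Conclusion.** The point holds as a defect of wording with a definite wrong result: under 7.1.2 together with 9.3.6, a clinically relevant abnormality in a sample taken before any exposure is counted as treatment-emergent if it is read after dosing. The expected effect is a few spurious treatment-emergent AEs that add noise to descriptive safety tables, balanced across arms in expectation. About 2 to 5 of 168 subjects is the size at an assumed 1% to 3%; the true rate could lie outside that range.

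The conclusion rests on two things that the documents do not state: that Visit 2 results come back after the first application, and that some subjects who were clean at Visit 1 have a clinically relevant value at Visit 2. It applies mainly to the ordinary two-visit schedule. The inconsistency among 7.1.2, 8.2.1, 9.3.4 and 9.3.6 exists whatever the rate.

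**What to change.** - **Section 7.1.2:** classify laboratory findings by sample collection time relative to the first application. A clinically relevant result from a pre-dose sample is medical history or baseline whenever it is reported; only a clinically relevant worsening after dosing is an AE.
- **Section 8.1.1:** replace the criterion of discovery before first application with the same collection-time criterion for laboratory abnormalities.
- **Section 9.3.6 and synopsis:** exclude findings from pre-dose samples from treatment-emergent AEs.
- **Section 7.1.4 and CRF completion guidelines:** medical history is updated at Visit 2 before randomization, so allow a later entry for a Visit 2 laboratory result.
- **Minor:** reconcile 5.6.4 and 7.1.2, which rest on Visit 1 results (7.1.2 wants them reviewed before Visit 2), with the local-laboratory alternative in 6.2.2. State whether local results meet the requirement for all measured analytes.

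The cost is wording in these sections and in the CRF guidelines. Collection times can be taken from laboratory records. No further tests, visits or subjects are needed.
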